6. Symptom-directed PE: on Day 1 (pre-dose and post-dose) and Day 2 in each dosing period to evaluate new symptoms before dosing and AEs after dosing.
7. BMI is calculated as wt (kg) / ht (m²).
8. VS (BP, HR, RR, T): at Screening; on Days -1, 1, and 2 in each dosing period; and at Final Visit after Dose 4, or ET. On Day 1 of each dosing period, VS at baseline (within 1 h before dosing) and at 1 h (±10 min), 2 h (±10 min), and 4 h (±10 min) after dosing.
9. Clinical laboratory testing with a minimum 4-h fast: HEM (Hgb, Hct, RBC, WBC with differential absolute count, platelet count); CHEM (creatinine with estimation of GFR, BUN, glucose, total bilirubin, direct bilirubin, AST, ALT, AP, total protein, albumin, electrolytes (sodium, potassium, chloride,

- bicarbonate (CO₂), magnesium); and dipstick UA (blood, protein, glucose): at Screening, Day -1, and Day 2, or ET. Clinical labs may not be repeated before Dose 1 if screening labs were completed ≤7 days before dosing. Clinical labs may be obtained at an unscheduled visit as indicated for work up of an AE.
10. Viral serology (HIV1/2 test, HBsAg, HCV antibody): at Screening.
 11. Serum pregnancy test in all women at Screening and within 24 h before each dosing period, and at the Final Visit, or ET. FSH only at Screening in post-menopausal women.
 12. 12-lead standard ECG with 10-sec rhythm strip: at Screening, Day -1, Day 1 [within 1 h before dosing, and at 1 h (±10 min), 2 h (±10 min), and 4 h (±10 min) after dosing], Day 2 (24 h ±2 h) or ET. At an Unscheduled Visit, a 12-lead standard ECG will be done only if needed for the evaluation of an AE.
 13. Continuous Holter ECG recorded from 1 h before dosing to 24 h after dosing in each dosing period. ECGs are extracted (three replicates per timepoint) before dosing (at 45, 30, and 15 min before dosing) and at 0.5 h, 1 h, 2 h, 3 h, 4 h, 6 h, 8 h, 12 h, and 24 h after dosing in each dosing period.
 14. Eligible subjects are randomized to a treatment sequence on Day 1 before receiving Dose 1. Randomization confirmed at each dosing period.
 15. Blood (plasma) PK samples: within 30 min before dosing, and at 0.5 h (±5 min), 1 h (±5 min), 2 h (±5 min), 3 h (±10 min), 4 h (±10 min), 6 h (±10 min), 8 h (±15 min), 12 h (±15 min), and 24 h (±2 h) after dosing in each dosing period, or ET if it occurs within 24 h of dosing.

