9.6. Clinical Laboratory Evaluations

Toxicity grade criteria for laboratory results can be found in [Table 4](#).

Unplanned clinical laboratory evaluations will be listed, but excluded from tabular and graphical summaries, except when calculating the maximum severity post-baseline.

Screening and safety clinical laboratory results (chemistry, hematology, and urinalysis) will be listed ([Listing 9](#), [Listing 10](#), [Listing 11](#)). Additionally, abnormal laboratory results (graded mild, moderate, or severe) will be listed in [Table 17](#), [Table 18](#), and [Table 19](#). Measurements outside of the normal range, but not graded as mild, moderate, or severe, will be flagged as “ONR” (outside normal range) in the listings.

Laboratory results will be summarized in tables and figures:

- Tabularly, by parameter, treatment, time point, and toxicity grade (including maximum severity post-baseline)
 - Chemistry Parameters: [Table 20](#)
 - Hematology Parameters: [Table 22](#)
 - Urinalysis Parameters: [Table 24](#)
- Tabularly, by summary statistics for change from baseline, reported by parameter, treatment, and time point
 - Chemistry Parameters: [Table 21](#)
 - Hematology Parameters: [Table 23](#)
- Graphically, using box plots showing the change from baseline by parameter, treatment, and time point
 - Chemistry Parameters: [Figure 13](#), [Figure 14](#), [Figure 15](#), [Figure 16](#), [Figure 17](#), [Figure 18](#), [Figure 19](#), [Figure 20](#), [Figure 21](#), [Figure 22](#), [Figure 23](#), [Figure 24](#), [Figure 25](#), [Figure 26](#), [Figure 27](#), [Figure 28](#)
 - Hematology Parameters: [Figure 29](#), [Figure 30](#), [Figure 31](#), [Figure 32](#), [Figure 33](#), [Figure 34](#), [Figure 35](#), [Figure 36](#), [Figure 37](#), [Figure 38](#)

The following parameters will be presented (in order):

- Chemistry: Sodium, Potassium, Magnesium, Chloride, CO₂, Glucose (Fasting), BUN, Creatinine, Estimated GFR, Total Protein, Albumin, AST, ALT, AP, Total Bilirubin, and Direct Bilirubin
- Hematology: Hemoglobin, Hematocrit, Erythrocytes, Leukocytes; absolute counts of Neutrophils, Lymphocytes, Monocytes, Eosinophils, and Basophils; and Platelets

- Urinalysis: Glucose by Dipstick, Protein by Dipstick, Hemoglobin by Dipstick, Erythrocytes by Microscopic Evaluation, Leukocytes by Microscopic Evaluation, Bacteria by Microscopic Evaluation

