Only laboratory parameters reported as continuous values will be included in tables of summary statistics for change from baseline and in box plots for change from baseline. Because microscopic urinalysis evaluation is only performed in subjects with an abnormal urine dipstick result, urinalysis parameters assessed by microscopic evaluation will be excluded from tables of summary statistics for change from baseline and in box plots for change from baseline. However, urinalysis parameters assessed by microscopic evaluation will be included in summaries of toxicity grading, where the toxicity grade will be imputed as “Normal” for subjects where microscopic evaluation was not performed.

Laboratory parameters that have grading criteria for both decreases (result lower than normal range and baseline measurement) and increases (result higher than normal range and baseline measurement) will be summarized separately by direction of change. For example, sodium will be summarized separately as “Sodium, Decrease” and “Sodium, Increase.”

In tables summarizing toxicity grading, maximum severity observed for the parameter after dosing and within the same dosing period will be summarized (max severity post-baseline). Results of maximum severity for “Any Parameter” will be included for chemistry, hematology, and urinalysis laboratory results. For “Any Parameter” results, the maximum severity across all laboratory parameters in the respective category is summarized by time point, and from maximum severity post baseline.

By protocol, up to one repeat of a planned clinical laboratory assessment is allowed (*Laboratory values that are outside the range of eligibility but are thought to be due to an acute condition or due to collection or laboratory error may be repeated once.*). If replicates for clinical laboratory results are present in the database, then only the second replicate will be summarized and reported. Replicates not used in the analysis will not be listed.

Viral serology screening results ([Listing 12](#)), urine toxicology and alcohol screening results ([Listing 13](#)), and serum hCG (Human Chorionic Gonadotropin) pregnancy test results ([Listing 14](#)) will be listed. If FSH is measured for any subject during the study, FSH will be included in [Listing 14](#).

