9.7. Vital Signs and Physical Evaluations

Toxicity grade criteria for vital signs can be found in [Table 3](#). Unplanned vital signs measurements will be listed, but excluded from tabular and graphical summaries, except when calculating the maximum severity post-baseline.

Vital signs results will be listed ([Listing 15](#)).

Vital signs results will be summarized in tables and figures:

- Tabularly, by parameter, treatment, time point, and toxicity grade (including maximum severity post-baseline) ([Table 25](#))
- Tabularly, by summary statistics for change from baseline, reported by parameter, treatment, and time point ([Table 26](#))
- Graphically, using box plots showing the change from baseline by parameter, treatment, and time point ([Figure 39](#), [Figure 40](#), [Figure 41](#), [Figure 42](#), [Figure 43](#))

The following parameters will be presented (in order): Systolic Blood Pressure, Diastolic Blood Pressure, Heart Rate, Respiratory Rate, and Temperature

Vital signs parameters that have grading criteria for both decreases (result lower than normal range and baseline measurement) and increases (result higher than normal range and baseline measurement) will be summarized separately by direction of change.

In tables summarizing toxicity grading, maximum severity observed for the parameter after dosing and within the same period will be summarized (max severity post-baseline). Results of maximum severity for “Any Parameter” will be included. For “Any Parameter” results, the maximum severity across all vital signs parameters is summarized by time point, and from maximum severity post baseline.

The study protocol allows measurements of vital signs to be repeated in the case of an abnormal measurement. The following rules will be used to decide which measurement to include in summaries if more than one replicate was entered into the clinical database.

- If the first replicate is normal, then it will be used for analysis
- If the first replicate is abnormal, and the second replicate is also abnormal, then the first replicate will be used if has a severity equal to or greater to the second replicate, or the second replicate will be used if the second replicate has a higher severity than the first replicate.
- If the first replicate is abnormal, the second replicate is normal, and a third replicate measurement was not performed, then the first replicate will be used in the analysis.

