- If the first replicate is abnormal, the second replicate is normal, and the third replicate is normal, then the second replicate will be used in the analysis.
- If the first replicate is abnormal, the second replicate is normal, and the third replicate is abnormal, then the first replicate will be used if has a severity equal to or greater to the third replicate, or the third replicate will be used if the third replicate has a higher severity than the first replicate.

Vital signs replicates not used in the analysis will not be listed.

PE findings will be listed ([Listing 16](#)).

9.8. 12-Lead Standard ECG

Toxicity grade criteria for 12-lead standard ECG parameters (PR and QTcF intervals) can be found in [Table 3](#). 12-lead standard ECG interval measurements ([Listing 17](#)), and overall interpretation and comments ([Listing 18](#)) will be listed. Unplanned 12-lead standard ECG measurements will be listed but excluded from tabular and graphical summaries.

12-lead standard ECG results will be summarized in tables and figures:

- Tabularly, 12-lead standard ECG change in overall interpretation from baseline will be shown by treatment and time point in [Table 27](#).
- Tabularly, by parameter, treatment, time point, and toxicity grade (including maximum severity post-baseline) ([Table 28](#))
- Tabularly, by summary statistics for change from baseline, reported by parameter, treatment, and time point ([Table 29](#))

-
- Graphically, using box plots showing the change from baseline by parameter, treatment, and time point ([Figure 44](#), [Figure 45](#), [Figure 46](#), [Figure 47](#), [Figure 48](#), [Figure 49](#))

The following parameters will be presented (in order): PR Interval; QRS Duration, QT Interval; QTcF Interval, RR Interval; ECG Mean Ventricular Rate.

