12.2.2 Displays of Adverse Events**Table 3: Toxicity Grading Tables – Clinical Adverse Events**

Clinical AEs	Mild (Grade 1)	Moderate (Grade 2)	Severe (Grade 3)
Vital Signs			
Fever - °C	38.0-38.4	38.5-38.9	>38.9
Fever - °F	100.4-101.1	101.2-102.0	>102.0
Tachycardia - bpm	101-115	116-130	>130 or ventricular dysrhythmias
Bradycardia - bpm	50-54 OR 45-50 if baseline <60	45-49 OR 40-44 if baseline <60	<45 OR <40 if baseline <60
Hypertension (systolic) - mmHg	141-150	151-160	>160
Hypertension (diastolic) - mmHg	91-95	96-100	>100
Hypotension (systolic) - mmHg	85-89	80-84	<80
Tachypnea – breaths per minutes	23-25	26-30	>30
12-Lead Standard ECG			
QTcF interval prolonged (msec)	Asymptomatic, QTcF 450-479 msec	Asymptomatic, QTcF 480-500 msec OR increase in interval 30-59 msec above baseline	Asymptomatic, QTcF >500 msec OR increase in interval ≥60 msec above baseline
PR interval prolonged (msec)	210-250 msec	>250 msec	Type II 2 nd degree AV block OR ventricular pause >3.0 sec
Cardiovascular			
Arrhythmia		Asymptomatic or transient signs; no medical intervention required	Recurrent and/or persistent signs; symptomatic medical intervention required
Hemorrhage	Estimated blood loss ≤100 mL	Estimated blood loss >100 mL; no transfusion required	Blood transfusion required
Respiratory			
Cough	Transient cough; no treatment required	Persistent cough; treatment required	Interferes with daily activities
Bronchospasm, Acute	Transient bronchospasm; no treatment required; forced expiratory volume in one second (FEV1) 71-80% of predicted peak flow	Requires treatment; normalizes with bronchodilator; FEV1 60-70% of predicted peak flow	No normalization with bronchodilator; FEV1 <60% of predicted peak flow
Dyspnea	Does not interfere with usual and social activities	Interferes with usual and social activities; no treatment	Prevents usual and social activities OR requires treatment
Gastrointestinal			
Nausea	No interference with normal activity	Some interference with normal activity	Prevents daily activities
Vomiting	No interference with activity OR 1-2 episodes in a 24 h period	Some interference with activity OR >2 episodes in a 24 h period	Prevents daily activity OR requires medical intervention

Clinical AEs	Mild (Grade 1)	Moderate (Grade 2)	Severe (Grade 3)
Diarrhea	2-3 loose or watery stools in a 24 h period	4-5 loose OR watery stools in a 24 h period	6 or more loose or watery stools in a 24 h period OR requires IV hydration OR requires medical intervention

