400 mg Moxifloxacin	Max Severity Post-Baseline	x	x	x	x	x	x	x
	1 h Post-dose	x	x	x	x	x	x	x

Dosing Period	Time Point	N	Mild		Moderate		Severe	
			n	%	n	%	n	%
	2 h Post-dose	x	x	x	x	x	x	x
	4 h Post-dose	x	x	x	x	x	x	x
	24 h Post-dose	x	x	x	x	x	x	x
	Follow-up ^a	x	x	x	x	x	x	x
	Pre-dose (Prior to Next Dose)	x	x	x	x	x	x	x
QTcF Prolongation								
Any Period	Max Severity Post-Baseline	x	x	x	x	x	x	x
	1 h Post-dose	x	x	x	x	x	x	x
	2 h Post-dose	x	x	x	x	x	x	x
	4 h Post-dose	x	x	x	x	x	x	x
	24 h Post-dose	x	x	x	x	x	x	x
	Follow-up ^a	x	x	x	x	x	x	x
	Pre-dose (Prior to Next Dose)	x	x	x	x	x	x	x
	Final Visit ^b	x	x	x	x	x	x	x
2 g Zoliflodacin	Max Severity Post-Baseline	x	x	x	x	x	x	x
	1 h Post-dose	x	x	x	x	x	x	x
	2 h Post-dose	x	x	x	x	x	x	x
	4 h Post-dose	x	x	x	x	x	x	x
	24 h Post-dose	x	x	x	x	x	x	x
	Follow-up ^a	x	x	x	x	x	x	x
	Pre-dose (Prior to Next Dose)	x	x	x	x	x	x	x
4 g Zoliflodacin	Max Severity Post-Baseline	x	x	x	x	x	x	x
	1 h Post-dose	x	x	x	x	x	x	x
	2 h Post-dose	x	x	x	x	x	x	x
	4 h Post-dose	x	x	x	x	x	x	x
	24 h Post-dose	x	x	x	x	x	x	x
	Follow-up ^a	x	x	x	x	x	x	x
	Pre-dose (Prior to Next Dose)	x	x	x	x	x	x	x
Placebo	Max Severity Post-Baseline	x	x	x	x	x	x	x
	1 h Post-dose	x	x	x	x	x	x	x
	2 h Post-dose	x	x	x	x	x	x	x
	4 h Post-dose	x	x	x	x	x	x	x
	24 h Post-dose	x	x	x	x	x	x	x
	Follow-up ^a	x	x	x	x	x	x	x
	Pre-dose (Prior to Next Dose)	x	x	x	x	x	x	x

Dosing Period	Time Point	N	Mild		Moderate		Severe	
			n	%	n	%	n	%
400 mg Moxifloxacin	Max Severity Post-Baseline	x	x	x	x	x	x	x
	1 h Post-dose	x	x	x	x	x	x	x
	2 h Post-dose	x	x	x	x	x	x	x
	4 h Post-dose	x	x	x	x	x	x	x
	24 h Post-dose	x	x	x	x	x	x	x
	Follow-up ^a	x	x	x	x	x	x	x
	Pre-dose (Prior to Next Dose)	x	x	x	x	x	x	x

Note: The “Max Severity Post-Baseline” rows indicate the maximum severity experienced by each subject at any time point post baseline within the period, including unscheduled assessments. N = number of subjects in safety population with the ECG measurement at the respective time point.

^a The “Follow-up” analysis time points refer to either Check-In visits for the next period (for analysis of treatments given in Period 1, 2, or 3) or to the Final Visit with Pre-dose 4 as baseline.

^b The “Final Visit” analysis time point uses the last measurement prior to the first dose as baseline.

Table 29: 12-Lead Standard ECG Change from Baseline – Summary Statistics by Parameter, Time Point, and Dosing Period

[Implementation Note: The following 12-lead standard ECG parameters will be summarized, in order:]

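### SAP 9.8 excludes unplanned standard ECGs that the Table 28 footnote counts in maximum severity; SAP 9.6 has a narrower conflict over unlisted laboratory replicates

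*SAP*

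**What the plan says.** **Standard ECGs.** The rule in SAP 9.8 is "Unplanned 12-lead standard ECG measurements will be listed but excluded from tabular and graphical summaries", with no exception. The same section names Table 28 as the tabulation by toxicity grade, with a maximum-severity row. The Table 28 footnote says that this row gives each subject's worst grade "at any time point post baseline within the period, including unscheduled assessments".

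The two neighbouring sections handle the same situation differently. SAP 9.6 has "Unplanned clinical laboratory evaluations will be listed, but excluded from tabular and graphical summaries, except when calculating the maximum severity post-baseline". SAP 9.7 has "Unplanned vital signs measurements will be listed, but excluded from tabular and graphical summaries, except when calculating the maximum severity post-baseline".

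**Laboratory replicates.** SAP 9.6 cites a sentence in protocol 8.2.1 that lets a value outside the eligibility range be repeated once if an acute condition or an error is suspected. It continues: "If replicates for clinical laboratory results are present in the database, then only the second replicate will be summarized and reported", and then "Replicates not used in the analysis will not be listed". SAP 9, by contrast, has every gradable laboratory, vital-sign and ECG result after the first dose graded, with the grade visible in the listings. The implementation note to Listing 9 says that the laboratory listings hold all laboratory results, unscheduled and screening ones included. SAP 9.7 also leaves unused vital-sign replicates out of the listings.

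**The concern.** Table 28 is where QTcF and PR severity from the standard ECGs is tabulated by treatment. The ECGs in dispute are not a random subset. Protocol Appendix A, footnote 12, says: "At an Unscheduled Visit, a 12-lead standard ECG will be done only if needed for the evaluation of an AE". The conflict therefore decides whether ECGs recorded because of a suspected problem count in that table. If the text stays as it is, the programmer chooses the rule, possibly with the results in view.

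For laboratory tests, a valid abnormal first value could be missing from the toxicity tables and from Listings 9 to 11. The adverse event entered for it under protocol 9.2.3 would remain, so the two outputs would disagree. Safety and tolerability of the 2 g and 4 g doses is a secondary objective, and changes in ECG parameters and laboratory values are among its outcome measures.

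**Working it through.** The plan gives no figure to reproduce, so the check sets text against text. The data values below are assumed, to show what each rule produces.

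**1. Standard ECGs**

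- SAP 9.8: unplanned ECGs enter no table.
- Table 28 footnote: unplanned ECGs enter the maximum-severity rows.
- Table 28 is one of the tables that 9.8 governs, so the two rules collide in those rows. They agree elsewhere.

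Assume a baseline QTcF of 440 msec, planned post-dose values all below 450 msec and less than 30 msec above baseline, and one unplanned ECG at 485 msec. The increase is 485 − 440 = 45 msec. SAP Table 3 defines Moderate as "Asymptomatic, QTcF 480-500 msec OR increase in interval 30-59 msec above baseline", so the unplanned ECG is Moderate on both limbs. Under 9.8 the subject has no grade in the maximum-severity row. Under the footnote the subject is Moderate.

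One such subject changes the row by 1/72 = 1.39 percentage points if all 72 subjects contribute to it. With 56 subjects it would be 1/56 = 1.79 points. The 56 is the evaluable number from the sample-size section and is used here only as a smaller denominator; Table 28 counts safety-population subjects with the ECG. SAP 13 prints percentages as whole numbers, so these appear as 1% and 2%.

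**2. Laboratory replicates**

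- *Source of the rule.* In protocol 8.2.1 the repeat sentence concerns eligibility values and comes after the range set for Screening and Day -1 of Period 1. It recurs in Appendix B under the screening exceptions. SAP 9.6 then words its rule for any replicate in the database.
- *Where it can affect a safety result.* Check-in laboratory tests for Periods 2 to 4 are planned, and SAP 3.3 uses them as the Follow-up point for the preceding treatment. Whether the eligibility sentence reaches them is unclear. Protocol 8.1.3 and Appendix A, footnote 2, reconfirm eligibility each period, but the continuation criteria in protocol 7.3 name no laboratory range.
- *Where it does not.* Unplanned laboratory tests are already listed and counted in maximum severity under SAP 9.6.

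Assume a baseline sodium of 144 mmol/L, a planned check-in value of 149 and a repeat of 146. SAP Table 4 makes 149–150 Grade 1. Under SAP 9 the 149 is Mild and appears in the listing. Under the replicate rule only the ungraded 146 is reported and the 149 appears nowhere. If the order is reversed (146, then 149), the replicate rule also reports Mild. The effect is therefore mainly, but not always, toward fewer abnormalities. Where the first value was a true laboratory error, dropping it from the summaries is a correction.

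**3. Vital signs**

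SAP 9 covers vital signs too, so the non-listing sentence in SAP 9.7 conflicts with it in the same way.

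**The case against.** On ECGs there is no good defence of the text as written. The best that can be said is that unplanned ECGs stay in Listing 17, so nothing is lost from the record. That limits the consequence but does not reconcile the two rules.

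On laboratory tests the opposing case is stronger. The sentence just before the replicate rule is about the permitted eligibility repeat, so replicates can fairly be read as meaning those repeats. A confirmatory draw at an unscheduled visit falls under the unplanned rule and is kept. The replicate rule can also be read as a specific exception to general statements elsewhere. This narrows the point to repeats of planned tests after the first dose. It does not remove it: neither SAP 9 nor the Listing 9 note states an exception, and 9.6 is not worded to stop at the first dose.

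A reader might infer that SAP 9.7 takes the worst vital-sign value and that laboratory tests should follow. The SAP does not support this. For abnormal, normal, normal, 9.7 uses the normal second reading. On equal severity it keeps the first, and a normal first reading is used whatever follows. A worst-value rule would also push change-from-baseline summaries toward extremes.

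**Conclusion.** The ECG rules contradict each other as written, and one of them must change. The laboratory conflict is real but conditional on a planned test being repeated after the first dose.

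The documents give no rate of unplanned ECGs or laboratory replicates, so the frequency of either problem is unknown and may be zero. The scale is 1.4 percentage points per affected subject in a Table 28 row of 72.

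A reader might go further and infer that graded events are lost, or that the trial's QT conclusion is at risk. Neither follows. Protocol 9.2.3 still sends laboratory abnormalities of Grade 1 or higher on the toxicity table to the adverse event data, and the primary QTcF analysis uses Holter recordings. This is a minor consistency correction.

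**What to change.** 1. **SAP 9.8.** Add the maximum-severity exception already in 9.6 and 9.7, so that the text agrees with Table 28 and ECGs taken to evaluate an adverse event count there.
2. **SAP 9.6, scope.** Limit the second-replicate rule to eligibility repeats before the first dose and to first values with a documented collection or laboratory error.
3. **SAP 9.6, grading.** Count any other replicate after the first dose in maximum severity, as 9.6 already does for unplanned tests. Attribute it to the preceding treatment, as SAP 3.3 does for post-dose records. Leave the choice of replicate for change from baseline as it is.
4. **Listings.** Show all laboratory replicates in Listings 9 to 11 with a used/not-used flag, and do the same for vital-sign replicates by amending the sentence in SAP 9.7.

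The cost is a few sentences, slightly longer listings and possibly slightly higher abnormality counts. No new data are needed, and the Holter analysis does not change. The edits should be made before database lock, so that the rule is not chosen after the results are seen.
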